1. Severe diabetes related chronic complications such as chronic renal failure, blindness, amputations, stroke, etc.
2. Concomitant chronic illnesses that would affect their participation in the program, i.e. cancer, debilitating diseases, etc.
3. Any other condition that would affect participant's basic mental health skills.
4. Type 1 diabetes or gestational diabetes.
5. Patients with abnormal hemoglobin, anemia or any condition that may affect red blood cell turnover. Any of these conditions may be detected through participants' history or through the laboratory report at study screening.
6. Signs or symptoms of metabolic decompensation (polyuria, polydypsia, polyphagia, unexplained weight loss, blurry vision, lethargy, etc.)

Elimination Criteria:

Development of any acute event during the study period that would affect participants' primary outcome at the discretion of the investigator, e.g. hyperosmolar coma, acute event of significant hyperglycemia or the use of certain medications like steroids.

Groups:

A total of 92 participants will be randomly assigned to one of the two study groups:

Group 1 – Intervention group – this group will complete activities described above. During scheduled follow-up clinical visits at months 3, 6, and 9, an additional A1c will be obtained. All measurements will be covered through the study grant if the patient does not have a recent laboratory result (2 weeks prior to the study visit) for the following test: A1c, lipid panel, ALT, AST, microalbumin, and chem 6 result.

Group 2 - Control Group –

This group will attend regular visits with their medical and education providers. As in the intervention group, these visits are expected to occur at 3, 6, and 9 months after the first visit. This group corresponds to the usual care that is provided at DHR.

Primary Outcome:

The primary outcome variable will be the change in hemoglobin A1c value from baseline to 6 months.

Sample Size:

We hypothesize that the decline in hemoglobin A1c value between the baseline and the six-month visit will be at least 0.5 percent greater in the intervention group than in the control group.

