The sample size and power calculation is based on preliminary results of our study where the study aimed at behavioral change. Assuming a mean reduction of 0.504 (SD= 1.2) in A1c in the intervention group and no change in the control group a sample size of 37 per group will be needed to detect this reduction with 80 % at 5% level of significance (one-sided) using the t-test. Assuming a 20% dropout, 46 study subjects per group (total 92) will be needed.

Recruitment:

Study Protocol

Study candidates will be identified at the partner site (DHR) where this protocol will take place. This will be done by creating flyers, videos, print and web-based ads, and letters to invite patients that attend the practice to join the study and/or by directly inviting patients that regularly attend the practice. Proper informed written consent will be obtained from all individuals prior to participation in the study.

Interventions:

a. Virtual diabetes self-management group

- i. Weekly conversations led by the diabetes educator (30-minute) using teleconsultation to deliver diabetes education and enhance adherence to treatment recommendations. These conversations will occur during the first 12 weeks of the intervention and will consist of the following elements: a) open question as to whether there is a particular item for discussion that the patient would like to address; b) review of blood glucose and physical activity results; c) review of the adherence to the four basic self-care behaviors (meal plan, physical activity, glucose monitoring and medications); d) identification of barriers to adhere to treatment recommendations; and e) provision of specific recommendations to overcome identified barriers. In order to provide diabetes education in a culturally and linguistically oriented manner, particularly to those patients with low health literacy, all participants in the virtual education program will be encouraged to listen to Rosa's or Jose's Story during the first 8 weeks of the intervention. These are audio-novellas developed by the Latino Diabetes Initiative at Joslin Diabetes Center to educate Latino patients with type 2 diabetes using the story telling method in a practical and engaging manner.

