The Joslin Diabetes Center's Institutional Review Board will be in charge of approving this protocol according to current clinical research guidelines.

Study Protocol

An informed consent for participation in the study will be generated to be approved by the IRB. This consent form will be given to all participants before the study begins. Only participants that have given full written consent will be able to participate in the study.

Adverse Events:

We don't anticipate any serious adverse events as this is a study that does not involve the use of any major procedure or the use of any pharmacologic intervention. The only potential adverse events are those related with answering questionnaires or drawing blood for the A1c test and other laboratories specified above.

Good Clinical Practice:

Whereas the primary objective of the protocol is to assess whether there is a significant difference in glycemic control with teleconsultations with the diabetes team at the patient's home, all participants in the study regardless of the **assigned study** group will be offered the best possible diabetes care according to current standards and approved treatment algorithms, particularly the recently published American Diabetes Association standards.

If at any point in time during the study, the investigators or practicing clinicians consider that it would be in the patient's best interest to terminate their participation in the study; this will be considered a priority.

Process and product study variables:

Primary outcome:

- **A1c levels:**

The values obtained through the laboratory at each of the participating sites will be used to evaluate the primary outcome of the study. The baseline A1c value will be used for eligibility for the study.

Other variables:

- **Demographic characteristics** (obtained at baseline)

The demographic variables of interest are: date of birth, years in the practice, household status (living with one or more persons, living alone), years of education, socioeconomic status, community of residence and insurance status.

- **Diabetes history** (obtained at baseline)

The variables of interest are: date of diagnosis, age at diagnosis, years with diabetes, family history of diabetes, diabetes specialist care and history of diabetes education.

- **Diabetes treatment plan** (obtained at baseline and during each clinical encounter in both groups and during the teleconsultations and telephone communications in the intervention group)

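### 37 per group does not give the stated 80% power for the between-group A1c comparison: about 56% if the control SD is also 1.2, and 50% to 73% for control SDs of 1.4 to 0.6

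*Combined protocol and SAP*

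**What the plan says.** The hypothesis appears under Purpose of Protocol and again under Sample Size: the fall in A1c from baseline to six months is to be "at least 0.5 percent greater in the intervention group than in the control group". The Groups section randomises 92 participants to two groups, and the primary outcome is the six-month change in A1c. The Good Clinical Practice section describes the primary objective as being to "assess whether there is a significant difference in glycemic control with teleconsultations".

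The inputs to the calculation are in the Sample Size section: "Assuming a mean reduction of 0.504 (SD= 1.2) in A1c in the intervention group and no change in the control group". The stated result is that "a sample size of 37 per group will be needed to detect this reduction with 80 % at 5% level of significance (one-sided", with a t-test as the method. The section then allows for attrition: "Assuming a 20% dropout, 46 study subjects per group (total 92) will be needed".

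The SD of 1.2 is attached to the intervention group. No SD is given for the control group's change. No baseline adjustment or correlation that would lower the SD is mentioned.

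**The concern.** A comparison of two group means carries sampling error from both groups. The calculation gives an SD for one group and describes the other only by its mean. With a similar SD in both groups, the variance of the difference is about twice that of a single mean, so the required number per group is also about twice as large. The figure of 37 looked too small for that reason.

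This is the only sample-size justification for the primary outcome. If the stated power is wrong, the chance of missing a real effect of the assumed size is well above the 20% that the plan implies. A non-significant result could then be misread as showing that the virtual program does not work.

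**Working it through.** **Inputs from the Sample Size section.** Difference d = 0.504, intervention SD s1 = 1.2, one-sided alpha 0.05, power 80%, n = 37 evaluable per group, dropout 20%.

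**Input not in the documents.** The control-group SD of change, s2. I take 1.2 (equal to the intervention group) as the main case and show 0.6 to 1.4.

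**Step 1: reproduce 37.** In a one-sample t-test on the intervention group's own change, the noncentrality is d × sqrt(n) / s1 with n − 1 degrees of freedom. At n = 37 it is 0.504 × 6.083 / 1.2 = 2.55, and power is 80.5%. At n = 36 power is 79.6%. The smallest n reaching 80% is therefore exactly 37. This amounts to treating the control change as a known zero. The protocol names no formula, so this origin is an inference.

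**Step 2: power of the two-group test at 37 per group.**

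SE = sqrt((s1² + s2²) / n), noncentrality = d / SE, df = 2n − 2 = 72. Power is the probability that a noncentral t exceeds the one-sided 5% critical value.

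With s2 = 1.2: SE = sqrt((1.44 + 1.44) / 37) = 0.279, and noncentrality = 0.504 / 0.279 = 1.81. Power is 55.7% (56.4% by the normal approximation).

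**Step 3: n per group for 80% power.** By the normal approximation, n = (1.645 + 0.842)² × (s1² + s2²) / d². With s2 = 1.2 this is 6.18 × 2.88 / 0.254 = 70.1, rounded up to 71. The exact t calculation agrees: 70 per group gives 79.6% and 71 gives 80.1%.

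**Step 4: vary the control SD.** Exact t, one-sided 5%:

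| Assumed control SD | SE at n = 37 | Power at n = 37 | n per group for 80% | Difference detectable with 80% power at n = 37 |
|---|---|---|---|---|
| 1.4 | 0.303 | 50% | 84 | 0.76 |
| 1.2 | 0.279 | 56% | 71 | 0.70 |
| 1.0 | 0.257 | 62% | 61 | 0.64 |
| 0.8 | 0.237 | 68% | 52 | 0.60 |
| 0.6 | 0.221 | 73% | 45 | 0.55 |

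Simulation with 200,000 runs per row gave the same powers to within 0.2 percentage points. At a control SD of 0.2, power is 80.3% with pooled degrees of freedom and 79.7% with Welch degrees of freedom. The stated 80% is therefore recovered only with almost no variability among controls.

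**Step 5: dropout.** 37 / 0.8 = 46.25, so 46 is the plan's figure to the nearest integer (47 if rounded up). If nobody dropped out, 46 per group with SD 1.2 in both groups would give 64% power. For 71 evaluable per group, 71 / 0.8 = 88.75, so 89 per group or 178 in total, which is 86 more than 92.

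**Step 6: sidedness.** The one-sided level is already used above. A two-sided 5% t-test with SD 1.2 in both groups needs 90 per group, so sidedness does not explain 37.

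**The case against.** The strongest point is that the documents do not give the control SD. The figures of 56%, 71 and 178 all rest on setting it to 1.2, and the range 0.6 to 1.4 has no source in the plan either. The size of the gap varies a good deal: at a control SD of 0.6, 45 evaluable per group would suffice, which is below the 46 enrolled, though not after 20% dropout. This stands as a limit on the size of the shortfall. It does not rescue the stated power, because no value in that range gives 80%. The phrase "no change in the control group" describes a mean. It does not say that each control participant's A1c stays fixed for six months. Controls enter with A1c of 8 to 14% and continue usual care, so an SD near zero is hard to defend beside 1.2 in the other group.

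A second reading takes 1.2 as the SD of the between-group contrast, which implies 1.2 / sqrt(2) = 0.85 per group. Then 37 per group gives 81% power. But the text ties the SD to the "mean reduction of 0.504 (SD= 1.2) in A1c in the intervention group", and under this reading the smallest sufficient n is 36, not 37.

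Two smaller points are fair. The words quoted from Good Clinical Practice name no comparator, so the between-group reading rests mainly on the hypothesis and on the two-group assumptions in the Sample Size section. The 44% miss rate applies to 37 evaluable per group; with all 46 evaluable and equal SDs it would be 36%.

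**Conclusion.** The concern holds. As written, 37 per group does not give 80% power for the comparison that the protocol sets out to make. Assuming a control SD of 1.2, power is about 56%, so an effect of 0.504 would be missed about 44% of the time. For control SDs of 0.6 to 1.4 the miss rate is 27% to 50%. That 37 per group falls short is firm for any control SD above about 0.2. The exact size of the shortfall depends on an SD that the plan must supply. That a one-sample formula was used is likely but unproven, and the conclusion does not need it.

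**What to change.** Correct the Sample Size section as follows.

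1. State the control-group SD of change that is assumed, and its basis.
2. Restate the power. With SD 1.2 in both groups, 37 evaluable per group gives about 56% power for 0.504 and 80% power for a difference of about 0.70; 80% power at 0.504 needs 71 evaluable per group.
3. Say which course is taken: keep 92 and justify the lower power, or raise enrolment to about 178 (with 20% dropout).
4. As a useful addition, commit to reporting the between-group difference with a two-sided 90% confidence interval, which matches the one-sided 5% test. State that a non-significant result will not be read as evidence against the hypothesised benefit unless the interval excludes 0.5. With SD 1.2 in both groups the half-width at 37 per group is 1.666 × 0.279 = 0.465, so this requires an observed difference below about 0.04 (0.5 − 0.465).

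Keeping 92 costs protocol wording only, but the plan must then admit that it is underpowered for 0.504. Keeping 80% power with equal SDs of 1.2 costs about 86 more participants. The protocol allows 12 months for enrolment and does not say whether that window or the grant could support them.

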- ii. Since the teleconsultations will only last 12 weeks, phone conversations with the diabetes educator will be implemented starting in the 4th month of the program. These will be 15-30 minute conversations and will occur at weeks 14, 15, 16, 17, 19, 21, and 23. The goal of the phone calls is to provide support to the patients and they will follow the same protocol as the weekly conversations described above.
- iii. A weekly text message will be sent to patients during the 6 months of the education program. These messages will focus on assessing and addressing participants' beliefs about common myths and misconceptions in the area of diabetes. The text message will present the myth of the week and request people's participation in responding whether the concept is true or false and will also provide the correct answer to the question presented the prior week.
- iv. Observation period: the third quarter of the intervention (months 6-9) will allow the observation of the residual effect of the virtual education program; therefore no contact or education will be planned for the last 3 months (months 7, 8 & 9). Patients will be followed in their corresponding clinics as usual.

b. In-person diabetes self-management education or control group

- i. Patients in this group will attend their regular clinical and education appointments as offered by the center.

The table below presents the timeline for the interventions discussed above.

	Months								
	1	2	3	4	5	6	7	8	9
Virtual education	4w R/J 4T	4w R/J 4T	4w 4T	4p 4T	2p 4T	1p 4T			

W=weekly teleconsultation

P=Phone conversation

R/J=Rosa or Jose's Story

T=Text message related to a diabetes myths and misconceptions

Study Procedures:

Before randomization, all participants will go through the following steps:

- 1) Eligible patients will have their standard follow-up clinical encounter with their corresponding health care provider.
- 2) Screening visit. At this time, the research assistant or study coordinator will obtain the baseline A1c measured through each site's laboratory and will review inclusion and exclusion criteria with study candidates to assess eligibility for the study. If the patient qualifies for the study, clinicians will not be aware of this at the time of the initial visit, so that this value does not influence their treatment at baseline and the intervention is left as the main explanatory variable.

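### The only stated test is one-sided at 5% without a reason given, and the 80% power attached to it is not reached for a two-arm comparison; state a two-sided 5% test with a 95% interval and restate the power

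*Combined protocol and SAP*

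**What the plan says.** The Sample Size section contains the document's only statement of a statistical test. Its inputs are "Assuming a mean reduction of 0.504 (SD= 1.2) in A1c in the intervention group and no change in the control group". From these it concludes that "a sample size of 37 per group will be needed", and describes the test and error rates as follows: this number "will be needed to detect this reduction with 80 % at 5% level of significance (one-sided) using the t-test". It then adds: "Assuming a 20% dropout, 46 study subjects per group (total 92) will be needed". The Groups section agrees: "A total of 92 participants will be randomly assigned to one of the two study groups".

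Two places bear on direction:

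- The hypothesis, given under Purpose of Protocol and again under Sample Size, is directional: the fall in A1c by six months is expected to be larger with the intervention, by 0.5 or more.
- Good Clinical Practice describes the primary objective without a direction: "to assess whether there is a significant difference in glycemic control with teleconsultations with the diabetes team".

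No analysis section states the primary test, its level and sidedness, the interval to be reported, or who is analysed. No reason is offered for testing one-sided at 5%.

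**The concern.** A one-sided test at 5% has a 5% chance of declaring a benefit when there is none. A two-sided 5% test has a 2.5% chance of an error in that direction. A one-sided test also cannot declare a difference in favour of the control, which fits poorly with an objective worded as a search for a significant difference.

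At stake is how a modest positive result would be read. At the number the plan expects to have after dropout, a benefit could be claimed while the usual 95% confidence interval still includes no effect. Because no analysis section fixes the test or the interval, the claim and the interval could be reported on different standards. The power attached to the one-sided test therefore also needs checking.

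**Working it through.** **Inputs.** All are from Sample Size: difference 0.504 (0.504 against no change), SD of change 1.2, one-sided 5%, 80% power, 37 per arm evaluable, 46 per arm enrolled. The control SD is not given; I assume 1.2 in both arms and vary it below.

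**Reproducing the plan's 37.** The standardised effect is 0.504 / 1.2 = 0.42.

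- Two-sample t-test, one-sided 5%, 80% power: 70.8, so 71 per arm.
- One-sample (within-group) t-test, one-sided 5%, 80% power: 36.4, so 37.

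The stated 37 is therefore what a one-sample calculation gives, about half of what the two-arm comparison needs. The dropout step is 37 / 0.8 = 46.25, stated as 46.

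**An observed difference of 0.504.** SE = 1.2 × √(2/n), df = 2n − 2, t = 0.504 / SE.

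| Analysed per arm | SE | t | One-sided p | Two-sided p | 95% CI |
|---|---|---|---|---|---|
| 37 | 0.279 | 1.806 | 0.0375 | 0.075 | -0.05 to 1.06 |
| 44 | 0.256 | 1.970 | 0.026 | 0.052 | -0.005 to 1.01 |
| 45 | 0.253 | 1.992 | 0.025 | 0.049 | 0.001 to 1.01 |
| 46 | 0.250 | 2.014 | 0.0235 | 0.047 | 0.007 to 1.00 |
| 71 | 0.201 | 2.502 | 0.0067 | 0.0135 | 0.11 to 0.90 |

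The planned effect passes one-sided and fails two-sided for about 32 to 44 analysed per arm. It passes both at 45 and 46, and comfortably at 71.

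**The band of results that pass one-sided only.**

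- 37 per arm: from 1.666 × 0.279 = 0.465 to 1.993 × 0.279 = 0.556. The planned 0.504 lies inside.
- 46 per arm: 0.416 to 0.497. The planned 0.504 lies just above.

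**Power for a true difference of 0.504 (two-sample, noncentral t).**

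| Per arm | One-sided 5% | Two-sided 5% | Loss from sidedness |
|---|---|---|---|
| 37 | 56% | 43% | 13 points |
| 46 | 64% | 51% | 13 points |

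At 37 per arm, the fall from the stated 80% is 24 points before sidedness is touched (80 − 56) and 13 points after (56 − 43). At 46 the figures are 16 and 13.

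**Sensitivity to the control SD, at 37 per arm.** SE = √((1.2² + control SD²)/37). The planned effect stays in the band for control SDs of about 0.96 to 1.39. Two-sided power runs from 62% (control SD 0.6) to 38% (control SD 1.4).

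**The case against.** The best case for the plan is that its hypothesis is directional and stated twice, and that the objective on A1c is also worded as improvement. A one-sided test is consistent with both. The non-directional wording comes from a clause introducing a statement about standard of care. This largely stands. A reader might infer that the test contradicts the trial's objective or cannot answer it; the documents do not support that. They support a wording inconsistency and a lenient level for which no reason is given. An expected direction does not explain why 5% rather than 2.5% is spent on it.

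A reader might also infer that one-sided testing by itself makes the planned effect a success with an interval that includes zero. That does not follow. In a two-arm trial that really had 80% power at one-sided 5% (71 per arm), an observed 0.504 gives an interval of 0.11 to 0.90. The pattern needs the small sample, and it disappears at 45 or 46 analysed per arm. It is conditional on 37, which is nevertheless the number the plan expects after dropout.

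It is tempting to argue that the control could do better because its heading reads "In-person diabetes self-management education or control group". The label is weak evidence. The line beneath it describes regular appointments as the center offers them, and the Groups section calls this arm usual care. A worse result with the intervention is possible, but the point does not rest on it.

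Finally, that the primary analysis will be one-sided is an inference from the sample-size sentence. It is the only test stated, but the document never says separately that this is how the primary outcome will be analysed.

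**Conclusion.** The concern holds in a limited form. The only stated test is one-sided at 5%, no reason is given, and it allows a 5% rather than 2.5% false-positive rate for benefit. With 37 analysed per arm, a result equal to the planned 0.504 would count as a success at one-sided p 0.038 while its 95% interval runs from -0.05 to 1.06. With all 46 per arm analysed the interval just excludes zero. No analysis set is defined, so the documents do not settle which case applies.

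The larger cause is the sample size: 37 per arm does not deliver the stated 80% for a two-arm comparison even one-sided. It would be wrong to read the 43% as the price of two-sided testing; that price is about 13 points, and the remainder is already missing. These figures assume SD 1.2 in both arms.

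**What to change.** State, in an analysis section, that the primary comparison of six-month A1c change is a two-sided 5% test, reported with a two-sided 95% confidence interval for the difference between arms. Word the primary objective and the hypothesis so that they agree with it.

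Replace the stated 80% with the power at the existing size: for a difference of 0.504 and SD 1.2 in both arms, about 43% with 37 per arm analysed and 51% with 46. Beside these, give the one-sided figures of 56% and 64%, so that the loss due to sample size is not attributed to the change in sidedness.

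This takes a few sentences and no added patients. The cost is about 13 points less power than the one-sided test and a plainly lower stated power. It does not repair the sample size: 80% power two-sided would need about 90 evaluable per arm, and whether to enlarge the trial is a separate decision.
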